## Abbreviations

Abbreviation	Definition
A/G	albumin/globulin ratio
ALP	alkaline phosphatase
ALT	alanine aminotransferase
AST	aspartate aminotransferase
AUC	area under the plasma concentration versus time curve
AUC 0-24 hr	area under the plasma concentration versus time curve from time zero to 24 hr
AUC 0-inf	area under the plasma concentration versus time curve from time zero to infinity
AUC 0-t	area under the plasma concentration-time curve from time zero to t (where t = the final time of detection)
BMI	body mass index
BUN	blood urea nitrogen
CI	confidence interval
CPK	creatine kinase, creatine phosphokinase
C max	maximum plasma concentration
CRP	C-reactive protein
CYP	cytochrome P450
C 0	initial plasma concentration
EDC	Electronic Data Capture
FAS	Full Analysis Set
GCP	Good Clinical Practice
γ-GTP	γ-glutamyltransferase
ICH	International Council for Harmonization of Technical Requirements for Pharmaceuticals for human use
ICIQ-SF	International Consultation on Incontinence Questionnaire-Short Form
I-QOL	Incontinence-Quality of Life
INR	international normalized ratio
IRB	institutional review board
ISD	intrinsic sphincter deficiency
IWRS	Interactive Web Response System
LDH	lactate dehydrogenase
LOCF	last observation carried forward
LPP	leak point pressure
MMRM	mixed-effect models for repeated measures
MUI	mixed urinary incontinence

Abbreviation	Definition
NA	noradrenaline
6-OHF	6 $\beta$ -Hydroxycortisol
PGI-I	Patient Global Impression-Improvement
POP	pelvic organ prolapse
PPS	Per Protocol Set
PT-INR	prothrombin time-international normalized ratio
free Q ave	Average urinary flow rate
free Q max	Maximum urinary flow rate
QOL	quality of life
QTcF	QT corrected for heart rate by Fridericia's formula
SOP	standard operating procedure
SUI	stress urinary incontinence
t 1/2	elimination half-time
t max	time to maximum plasma concentration
TOT	Trans-Obturator Tape
TVT	Tension-free Vaginal Tape
ULN	upper limit of normal
UUI	urgency urinary incontinence
VD	vaginal distention
Vdss	distribution volume at steady state
X 6-OHF /X F	ratio of urinary 6 $\beta$ -hydroxycortisol to cortisol
X 6-OHF /AUC F	ratio of urinary 6 $\beta$ -hydroxycortisol to cortisol area under the plasma concentration versus time curve (AUC)

## Synopsis

Name of Sponsor:	Taiho Pharmaceutical Co., Ltd.
Name of Investigational Product:	TAS-303 [REDACTED]
Non-proprietary name:	-
Title of Study:	
An early phase II study of TAS-303 in female patients with stress urinary incontinence	
Protocol Number:	10060050
Phase of Development:	Phase IIa
Indication:	Stress urinary incontinence (SUI)
Background/Rationale:	
SUI is a complaint of involuntary leakage of urine at the time of exertion or exercise, or during sneezing or coughing.
 
According to Clinical Guideline for Female Lower Urinary Tract Symptoms, although anatomical factors of SUI cannot be improved by medication, resting urethral pressure has been reported to be lower in SUI patients than in women at the same age without urinary incontinence and therefore, theoretically, SUI can be treated by improving the low urethral closure pressure.
 
[REDACTED]
 
[REDACTED]
 
[REDACTED]

Study Objective/Endpoints:	
Primary: To examine the efficacy of TAS-303 using the rate of change in the number of urinary incontinence as an index and placebo as control in female patients with SUI
 
Secondary:
 
 
(1) To examine the efficacy of TAS-303 using changes in the variables including the International Consultation on Incontinence Questionnaire-Short Form (ICIQ-SF) score or the Incontinence Quality of Life (I-QOL) score as indices and placebo as control in female patients with SUI
 
(2) To examine the dose response of TAS-303 in improvement of urinary incontinence in female patients with SUI in an exploratory manner
 
(3) To examine the safety of TAS-303 using the status of onset of adverse events and other indices in female patients with SUI
 
 
Primary Endpoint:
 
 
• Rate of change in mean number of urinary incontinence per 24 hours (Week 8 in treatment period)
 
 
Main Secondary Endpoints:
 
 
• Mean number of urinary incontinence per 24 hours
 

	
 
Amount of urinary incontinence by 1-hour pad test
 
Mean number of used pads per 24 hours
 
ICIQ-SF score
 
Patient Global Impression-Improvement: PGI-I
 
I-QOL score
 
Status of onset of adverse events and adverse reactions
 

Study Design:	
This clinical trial is a multicenter randomized double-blind placebo-controlled parallel-group study with central enrollment for the examination of efficacy and safety of TAS-303 in female patients with SUI. The design of this study is shown in the following figure. This study consists of a single-blind observation period, a double-blind treatment period and a follow-up observation period. In the observation period, the study drug (placebo) is orally administered once daily for 3 weeks. Subjects are randomly assigned to the study drugs to be given during the treatment period with a ratio of TAS-303 3 mg group: TAS-303 6 mg group: Placebo group of 1:1:1. In the treatment period, the study drugs are orally administered once daily for 8 weeks. Patients are asked to visit the office 4 and 8 weeks after the start of the treatment period (enrollment in the treatment period) to perform specified observation and tests. Follow-up observation is performed 2 to 4 weeks after the last administration of the study drugs.
  
The diagram illustrates the study timeline across five phases:
 
 
Phase 1: Enrollment in observation period (Week -3 W to -10 days).
 
Phase 2: Enrollment in treatment period (Allocation) (Week 0 to 3 W).
 
Phase 3: Treatment period (double-blind) (Week 4 W to 8 W). This phase includes three groups: TAS-303 3 mg once-daily administration (p. o.), TAS-303 6 mg once-daily administration (p. o.), and Placebo once-daily administration (p. o.).
 
Phase 4: Follow-up observation period (Week 10-12 W).
 
Phase 5: Follow-up observation (Week 10-12 W +3 days).
 

Study Status	
Study Completion Date (Anticipate): March, 2018
 
Region/Location: Japan

No. of Patients Planned:	In this study, central enrollment of 250 patients in the treatment period is planned.
Eligibility of patients:	
Inclusion Criteria at the Time of Enrollment in Observation Period:
 
 
Female outpatients who gave written consent by themselves
 
Aged 20 years or older and younger than 80 years at the time of consent
 
Have symptoms of SUI for at least 12 weeks before enrollment in the observation period
 
Considered by the Investigator or Sub-investigator to be able to go to the bathroom and keep an accurate urination record by themselves
 
Meet all the following conditions for ICIQ-SF at the time of the enrollment in the observation period 
 
1) Selection of the answer, "about once a day" (3 points), or those with higher scores for Q1
 
2) Selection of the answer, "small amount" (2 points), or those with higher scores for Q2
 
3) Selection of the answer, leaks "when I cough or sneeze" or leaks "while I am moving my body or exercising" for Q4
 
 
 

	
 
The amount of urinary incontinence exceeds 2.0 g in a 1-hour pad test at the time of the enrollment in the observation period.
 
 
Inclusion Criteria at the Time of Enrollment in Treatment Period:
 
 
Fulfillment of all the following conditions has been indicated in the information in the urination record for 7 days immediately before the enrollment in the treatment period. 
 
1) 1 or more mean number of urinary incontinence per 24 hours
 
2) Number of SUI > number of urgency urinary incontinence (UUI)
 
3) Ten or less mean number of daytime urination per day and 2 or less mean number of night-time urination per day
 
4) 70% or higher rate of entry in urination record (status of urinary incontinence)
 
 
 
Meet all the following conditions for ICIQ-SF at the time of the enrollment in the treatment period 
 
1) Selection of the answer, "about once a day" (3 points), or those with higher scores for Q1
 
2) Selection of the answer, "small amount" (2 points), or those with higher scores for Q2
 
3) Selection of the answer, leaks "when I cough or sneeze" or leaks "while I am moving my body or exercising" for Q4
 
 
 
 
Main Exclusion Criteria at the Time of Enrollment in Observation Period:
 
 
Symptoms of UUI were considered by the Investigator or Sub-investigator to be more predominant than those of SUI
 
History of surgical treatment for urinary incontinence (Trans-Obturator Tape [TOT] procedure, Tension-free Vaginal Tape [TVT] procedure, etc.)
 
Have accompanying pelvic organ prolapse quantification (POP-Q) stage II or more severe pelvic organ prolapse (POP) or underwent surgical repair of POP within 180 days before the enrollment in the observation period
 
Accompanying lower urinary tract obstruction
 
Accompanying urinary tract infection (cystitis, etc.), urolithiasis (ureteral calculus, urethral calculus, vesical calculus, etc.), urethral diseases (urethral polyp, urethral diverticulum, etc.) or interstitial cystitis, or a history of recurrent urinary tract infection (3 or more incidents within 180 days before the consent)
 
Diagnosis of neurogenic bladder
 
Difficulty in undergoing pad test (going up and down stairs, etc.)
 
Accompanying central nervous system disorders (dementia, etc.) that make it impossible to answer the questionnaire
 
Accompanying angle-closure glaucoma
 
100 mL or more residual urine volume measured at the time of the enrollment in the observation period
 
Delivery within 1 year before the enrollment in the observation period
 
Started physical therapy (pelvic floor muscle training, feedback training, biofeedback training, vaginal cone, bladder training, electric stimulation therapy, magnetic stimulation therapy, etc.) within 30 days before the enrollment in the observation period
 
Pregnant or nursing women, or women of childbearing potential with
 

--	--

	
positive pregnancy test (urine or serum) within 7 days before the enrollment in the observation period
 
 
Fertile patients who do not agree to practice contraception during their participation in the study and for 40 days after the completion of the treatment with the study drugs
 
 
Main Exclusion Criteria at the Time of Enrollment in Treatment Period:
 
 
Less than 80% compliance with the treatment with the study drugs during the observation period
 
Urinary incontinence symptoms at the time of enrollment in the treatment period were considered by the Investigator or Sub-investigator to have improved greatly compared with those at the time of the enrollment in the observation period (50% or greater improvement in the mean number of urinary incontinence per 24 hours, etc.).
 
Symptoms of UUI were considered by the Investigator or Sub-investigator to be more predominant than those of SUI based on the information in the urination record for 7 days immediately before the enrollment in the treatment period.
 
100 mL or more residual urine volume measured at the time of the enrollment in the treatment period
 
Pregnant or nursing women, or women of childbearing potential with a positive pregnancy test (urine or serum) within 7 days before the enrollment in the treatment period
 

Administration Regimens:	
Observation Period: Placebo is orally administered once daily for 3 weeks.
 
Treatment Period: Three or 6 mg of TAS-303, or placebo is orally administered once daily for 8 weeks.

Study Participation Period:	
Study Participation Period: Period from the acquisition of written consent to the completion of the follow-up observation period
 
Observation Period: Period from the enrollment in the observation period up to the enrollment in the treatment period (the enrollment in the treatment period is implemented 3 weeks after the enrollment in the observation period)
 
Treatment Period: Period from the enrollment in the treatment period to the visit at Week 8 in the treatment period
 
Follow-up Observation Period: Period after the visit at Week 8 in the treatment period to the completion of the follow-up observation (implemented 2 to 4 weeks after the completion of Week 8 of the treatment period)

Statistical Methods:	
Analysis Populations:
 
The analysis populations of this study are defined as follows:
 
  
 Analysis Set	Definition	
   
 Screened Patients	A group of all patients who gave consent	
 
 Enrolled Patients in observation period	A group of all patients enrolled in the observation period of this study	
 
 Enrolled Patients in treatment period	A group of all patients enrolled in the treatment period of this study	
 
 All Treated Patients	A group of patients who took the study drugs at least once among those enrolled in the observation period	
 
 Full Analysis Set (FAS)	A group of patients who took the study drugs for the treatment period at least once and have at least 1 efficacy endpoint before the start of the treatment period and during the treatment period among those enrolled in the treatment period	
 
 Per Protocol Set (PPS)	 
A group of patients in FAS except for those who meet the following criteria
 
 
(1) Shown not to meet inclusion criteria
 
(2) Shown to meet exclusion criteria (criteria affecting efficacy evaluation)
 
(3) Less than 80% compliance with the treatment during treatment period
 
(4) Less than 70% entry rate in urination record (status of urinary incontinence) at Week 8 of the treatment period
 
(5) Use of prohibited concomitant drugs or therapies considered to influence efficacy evaluation
 
 	
  
	Analysis Set	Definition	Screened Patients	A group of all patients who gave consent	Enrolled Patients in observation period	A group of all patients enrolled in the observation period of this study	Enrolled Patients in treatment period	A group of all patients enrolled in the treatment period of this study	All Treated Patients	A group of patients who took the study drugs at least once among those enrolled in the observation period	Full Analysis Set (FAS)	A group of patients who took the study drugs for the treatment period at least once and have at least 1 efficacy endpoint before the start of the treatment period and during the treatment period among those enrolled in the treatment period	Per Protocol Set (PPS)	
A group of patients in FAS except for those who meet the following criteria
 
 
(1) Shown not to meet inclusion criteria
 
(2) Shown to meet exclusion criteria (criteria affecting efficacy evaluation)
 
(3) Less than 80% compliance with the treatment during treatment period
 
(4) Less than 70% entry rate in urination record (status of urinary incontinence) at Week 8 of the treatment period
 
(5) Use of prohibited concomitant drugs or therapies considered to influence efficacy evaluation
 

Analysis Set	Definition														
Screened Patients	A group of all patients who gave consent														
Enrolled Patients in observation period	A group of all patients enrolled in the observation period of this study														
Enrolled Patients in treatment period	A group of all patients enrolled in the treatment period of this study														
All Treated Patients	A group of patients who took the study drugs at least once among those enrolled in the observation period														
Full Analysis Set (FAS)	A group of patients who took the study drugs for the treatment period at least once and have at least 1 efficacy endpoint before the start of the treatment period and during the treatment period among those enrolled in the treatment period														
Per Protocol Set (PPS)	
A group of patients in FAS except for those who meet the following criteria
 
 
(1) Shown not to meet inclusion criteria
 
(2) Shown to meet exclusion criteria (criteria affecting efficacy evaluation)
 
(3) Less than 80% compliance with the treatment during treatment period
 
(4) Less than 70% entry rate in urination record (status of urinary incontinence) at Week 8 of the treatment period
 
(5) Use of prohibited concomitant drugs or therapies considered to influence efficacy evaluation
 
														

#### **Primary Endpoint:**

The following analyses are performed regarding the rate of change in mean number of urinary incontinence per 24 hours at Week 8 of the treatment period from baseline, which is the primary endpoint.

- (1) Main analysis
  - In PPS, the difference between the TAS-303 6 mg group and the placebo group and the difference between the TAS-303 3 mg group and the placebo group are tested by t test using the two-sided significance level of the entire test of 5%. To consider multiplicity, the significance level for each comparison is adjusted by Hochberg's method.
- (2) Sensitivity analysis of main analysis
  - The evaluation in (1) is performed in FAS. Missing values are imputed using last observation carried forward (LOCF).
- (3) Secondary analysis of primary endpoint

The following analyses are performed in FAS and PPS.

  - Summary statistics are calculated for each treatment group. Missing values are not imputed.
  - The rate of change from baseline in mean number of urinary

	
incontinence per 24 hours for each week was analyzed using mixed-effect models for repeated measures (MMRM) to estimate the therapeutic effect of TAS-303 at Week 8 of the treatment period.
 
 
- In PPS and FAS, intergroup comparison is performed by Wilcoxon rank sum test. Missing values are imputed by LOCF.
 
 
(4) Analysis by allocation factor
 
 
- The primary endpoint is analyzed for each condition of urinary incontinence (SUI and mixed urinary incontinence [MUI]).
 
- The primary endpoint is analyzed for each category of mean number of urinary incontinence per 24 hours (less than 2/day and 2 or more/day).
 

Sample Size Justification:	
Target number of patients: 250 to be enrolled in the treatment period
 
This study is the first study that evaluates the efficacy of TAS-303 for the treatment of urinary incontinence. The number of subjects was determined, assuming that efficacy comparable to that of duloxetine can be expected based on the results of nonclinical studies.
 
Based on the mean rate of change in the number of urinary incontinence of -62.28% in the duloxetine group and -41.86% in the placebo group from the data of a clinical trial of duloxetine, [REDACTED] the difference between the TAS-303 6 mg or 3 mg group and the placebo group in the rate of change in the number of urinary incontinence, which is the primary endpoint of the present study, was assumed to be -20%. From the standard deviation of 33.73% in the duloxetine group and 32.08% in the placebo group in the above study data, the standard deviation common in two groups was assumed to be 35%. Using the two-sided significance level of the entire test of 5% and the two-sided significance level of each test of 2.5% by Bonferroni's method, when the statistical power is specified as 90% and the rate of withdrawal in the treatment period as about 5%, the number of subjects necessary for the confirmation of a significant difference between the TAS-303 group and the placebo group is approximately 250 (83 per group).

Table 1 Evaluation and Test Items

Acquisition of consent			
Date of acquisition of consent			
Patient background			
Gender	Date of birth	Age *1	
Race	Height	Body weight	
BMI *2	History of clinical trial participation (within past 90 days)		
Past history (within past 180 days)	Complication		
Onset timing of SUI (year)	Condition of urinary incontinence (SUI/MUI) *3		
Presence or absence of menopause	Number of delivery (natural/cesarean section)		
History of previous treatment	Menstrual cycle		
Presence or absence of use of incontinence pad	History of POP surgical repair		
Patient enrollment			
Patient identification code	Patient number	Drug number	
Subjective and objective findings			
Vital signs			
Pulse rate	Blood pressure (systolic, diastolic)	Body temperature	
Compliance with treatment with study drugs			
Concomitant medications and therapies			
12-lead electrocardiography			
Heart rate	QTcF interval		
Hematological tests			
Red blood cell count	Hemoglobin	Hematocrit	Platelet count
White blood cell count	Neutrophil	Eosinophil	Basophil
Lymphocyte	Monocyte	PT-INR	
Serum chemistry			
AST	ALT	ALP	BUN
Albumin	Creatinine	Na	Cl
K	T-Bil	Direct bilirubin	Total protein
CRP	CPK	LDH	γ-GTP
Blood sugar	Triglyceride	Total cholesterol	A/G
Urinalysis			
Protein	Occult blood	Glucose	Urobilinogen
Pregnancy test *4	Serum or urinary β-human chorionic gonadotropin		
Evaluation of symptom scores			
ICIQ-SF	PGI-I		
Evaluation of QOL score			
I-QOL			
Urination record			
Status of urinary incontinence, time and date	Presence or absence of pad change		
Urination time and date			
Pad test			
1-hour pad test			
Measurement of urinary flow			
Maximum urinary flow rate (free Q max )	Average urinary flow rate (free Q ave )		
Voided volume	Time of voiding		
Measurement of residual urine volume			
Evaluation of adverse events			

[figure not shown]
[figure not shown]
\*1: Automatically calculated from date of birth

\*2: Automatically calculated from height and body weight

\*3: Determined from the content of Q4 of ICIQ-SF

\*4: Required. When at least 1 year has passed after menopause or when the possibility of pregnancy is medically denied, the test is not necessary.

Table 2 Observation and Test Schedule

Timing	At enrollment in observation period	Observation period 	At enrollment in treatment period	Treatment period 				Follow-up observation 	At discontinuation 
				7 days before enrollment in treatment period	7 days before Week 4 visit	Week 4	7 days before Week 8 visit	Week 8	
Visit	1	2	3	4	5				
Week	-3		1			4		8	10 to 12
Acquisition of consent	X 								
Patient background survey	X		X						
Enrollment	X		X						
Study drugs	Prescription	X	X			X			
Collection of remaining drugs			X		X		X		X
Confirmation of compliance			X		X		X		X
Subjective and objective findings	X		X		X		X	X	X
Blood pressure, pulse rate and body temperature measurement	X 		X		X		X	X	X
12-lead electrocardiography	X 		X					X	X
Laboratory test 	X 		X		X		X	X	X
Pregnancy test 	X		X					X	X
Urination record	Distribution	X	X		X				
Collection			X		X		X		X
Confirmation of entry			X		X		X		X
Record of status of urinary incontinence									
Record of number of used pads									
Record of number of urinations									
1-hour pad test	X		X				X		X
ICIQ-SF evaluation	X		X		X		X		X
PGI-I evaluation			X		X		X		X
I-QOL evaluation			X		X		X		X
Urinary flow test			X				X		X
Measurement of residual urine volume by ultrasonography	X 		X				X		X
Concomitant drugs and therapies 									X
Evaluation of adverse events 									X

1. Acquisition of consent: Consent is obtained within 28 days before the enrollment in the observation period.

2. Laboratory test: Hematological tests, serum chemistry and urinalysis are performed.

3. Pregnancy test: Required. When at least 1 year has passed after menopause or when the possibility of pregnancy is medically denied, the test is not necessary. The pregnancy test (serum or urine) before the enrollment must be negative.

4. Concomitant drugs/therapies, evaluation of adverse events: Investigated from the acquisition of consent to the completion of the follow-up observation period.
5. Acceptable range of observation period: Observation period is 3 weeks in principle, but up to 4 weeks is permitted.
6. Acceptable range of timings of visits in treatment period: Week 4 and Week 8 visits  $\pm$  3 days from the scheduled dates are permitted.
7. Follow-up observation: Observation is performed 2 to 4 weeks after the completion of Week 8 of the treatment period. When the treatment is discontinued, it is performed 2 to 4 weeks after the last administration of the study drugs.
8. In cases of discontinuation: Specified observation and tests are performed as much as possible.
9. When the specified observation and tests were performed within 14 days before the enrollment, even if it was before the consent, the results can be used as the data at the time of the enrollment in the observation period.

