### 3. Overview of Study Design

This clinical trial is a multicenter randomized double-blind placebo-controlled parallel-group study with central enrollment for the examination of efficacy and safety of TAS-303 in female patients with SUI. The design of this study is shown in [Figure 3-1](#). This study consists of a single-blind observation period, a double-blind treatment period and a follow-up observation period.

The procedures of the observation period are implemented in patients considered to be eligible in the enrollment in the observation period after written consent. Single-blind design is used for the administration of the study drug during the observation period. In the observation period, the study drug (placebo) is orally administered once daily for 3 weeks. After the completion of the observation period, the patients considered to be eligible in the enrollment in the treatment period are shifted to the treatment period. Double-blind design is used for the administration of the study drugs during the treatment period. Subjects are randomly assigned to the study drugs to be given during the treatment period with a ratio of TAS-303 3 mg group: TAS-303 6 mg group: Placebo group of 1:1:1. In order to achieve a balance among groups, dynamic allocation is performed using allocation factors (mean number of urinary incontinence per 24 hours [less than 2/day, 2 or more/day] and condition of urinary incontinence [SUI, MUI]). In the treatment period, the study drugs (3 mg of TAS-303, 6 mg of TAS-303 or placebo) are orally administered once daily for 8 weeks. Patients are asked to visit the office 4 and 8 weeks after the start of the treatment period (enrollment in the treatment period) to perform specified observation and tests. Follow-up observation is performed 2 to 4 weeks after the last administration of the study drugs. When an adverse event is considered to be an adverse reaction at the time of the follow-up observation, follow-up investigation is performed as much as possible until the symptoms (including abnormal laboratory test values) are confirmed to have resolved to achieve the condition before the onset or to be resolving.

[figure not shown]

Figure 3-1 Study Design

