### **5.1.8 12-lead Electrocardiography**

Twelve-lead electrocardiography is performed at the timings shown in [Table 5-2](#). It should be performed keeping patients at rest, using the same method for each patient.

The Investigator or Sub-investigator is responsible for assessing the results of electrocardiography. All the abnormal findings considered to be clinically significant compared with baseline must be recorded as adverse events. The evaluation methods of adverse events shown in [Section 12](#) are used.

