## 7.2 Total Blood Volume

The volume of blood collected in this study is shown in [Table 7.2-1](#). The total volume of blood collected from each patient is approximately 90 mL.

Table 7.2-1 Volume of Blood Collected during Study Participation Period

Item	Number of blood collection	Volume of blood collected per collection	Total volume of collected blood
Laboratory test	5	Approximately 15 mL	Approximately 75 mL
Pregnancy test	3 (for blood test)	Approximately 5 mL	Approximately 15 mL
Total	5	-	Approximately 90 mL

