8.3.2. Laboratory Test Values

- Changes in laboratory parameters (quantitative test) from the baseline will be graphically presented.
- Summary statistics for laboratory test parameters (quantitative test) at each evaluation time point will be calculated.
- Frequency of each laboratory parameter (urine qualitative test) at each evaluation time point will be tabulated.

8.3.3. 12-Lead ECG

- Summary statistics for the observed value of the QTcF interval and heart rate at each evaluation time point will be calculated.
- Summary statistics for change from baseline in the observed value of the QTcF interval and heart rate at each evaluation time point will be calculated.
- For amounts of changes in measured values of the QTcF interval and heart rate from values immediately before the start of treatment to each evaluation time point, student's t-test will be conducted using the placebo group as the control.
- The observed value of the QTcF interval at each evaluation time point was divided into categories (≤ 450 msec, > 450 msec and ≤ 480 msec, > 480 msec, and ≤ 500 msec, > 500 msec), and the frequency of each category will be tabulated.
- Change from baseline in the observed value of the QTcF interval and heart rate at each evaluation time point was divided into categories (QTcF interval, ≤ 30 msec, > 30 msec, and ≤ 60 msec, > 60 msec: heart rate <5 bpm, ≤ 5 bpm), and the frequency of each category will be tabulated.
- The incidence of abnormal variations in 12-lead ECG will be calculated.
- A list of patients with abnormal 12-lead ECG changes will be prepared.

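### With its columns fixed by the protocol's own counts, Synopsis Table 2 gives treatment completers no ECG on drug, so the QTcF comparison with placebo may describe patients off drug

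*Protocol*

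**What the plan says.** **Schedule.** The timing of "12-lead electrocardiography" appears only in the schedule tables. Section 5.1.8 names no visit: "Twelve-lead electrocardiography is performed at the timings shown in" Table 5-2. Section 2.3.2.2 lists the ECG as a safety endpoint without times, although it gives times for urinary flow, residual urine and number of urinations.

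**Follow-up.** Section 3 says: "Follow-up observation is performed 2 to 4 weeks after the last administration of the study drugs". Footnote 7 of Synopsis Table 2 dates the visit from the end of treatment: "Observation is performed 2 to 4 weeks after the completion of Week 8 of the treatment period". For a completer both place it after dosing has ended.

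**Discontinuation.** The ECG is also marked in the discontinuation column, subject to footnote 8: "In cases of discontinuation: Specified observation and tests are performed as much as possible".

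**Analysis.** Protocol 13.1.3.3 (Safety Analysis, item 4) plans summaries and categories of QTcF and of the change in QTcF and heart rate. SAP 8.3.3 sets the QTcF categories up to above 500 msec and the change categories up to above 60 msec. It adds Student's t-tests against placebo: "For amounts of changes in measured values of the QTcF interval and heart rate from values immediately before the start of treatment". Neither document says which visits supply the ECG. SAP 8.3.5 and 8.3.6, by contrast, name Week 8 for uroflowmetry and residual urine.

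**The concern.** TAS-303 inhibits noradrenaline reuptake. The protocol's tables for drugs with the same action (section 1.4.2) list palpitations, tachycardia, increased heart rate and arrhythmia. The ECG analyses are therefore a substantive part of the safety evaluation.

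If completers have their only post-baseline ECG weeks after the last dose, the change tables and the t-tests compare groups of whom nearly all are no longer being dosed. A finding of no difference from placebo could then occur whether or not the drug alters QTcF during dosing, yet SAP 8.3.3 would present it as an ordinary drug-placebo comparison. No other scheduled assessment supplies on-treatment QTcF.

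**Working it through.** **1. Inputs.** Each row of Synopsis Table 2 was split into its cells after the row label. The marks fall as follows.

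| Row | Cells marked |
|---|---|
| Vital signs | 1, 3, 5, 7, 8, 9 |
| ECG | 1, 3, 8, 9 |
| Laboratory | 1, 3, 5, 7, 8, 9 |
| Pregnancy test | 1, 3, 8, 9 |
| 1-hour pad test | 1, 3, 7, 9 |
| ICIQ-SF | 1, 3, 5, 7, 9 |
| Urinary flow | 3, 7, 9 |
| Residual urine | 1, 3, 7, 9 |

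Table 7.2-1 gives 5 laboratory collections of about 15 mL, 3 pregnancy-test collections of about 5 mL, and about 90 mL in total. Section 2.3.2 places the pad test, urinary flow and residual urine at Week 8 and at no other post-baseline time, and ICIQ-SF at Weeks 4 and 8.

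**2. Which cell is which visit.** The printed headings do not line up with the marks: the Week row puts Week 4 over cell 6 and Week 8 over cell 8. Two readings were tested.

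- *Reading A: cell 5 = Week 4, cell 7 = Week 8, cell 8 = follow-up, cell 9 = discontinuation.* Scheduled laboratory tests are cells 1, 3, 5, 7, 8 = 5. Scheduled pregnancy tests are cells 1, 3, 8 = 3. Blood volume is 5 × 15 + 3 × 5 = 75 + 15 = 90 mL, which reproduces the stated total. The pad test, urinary flow and residual urine fall at Week 8, and ICIQ-SF at Weeks 4 and 8, as section 2.3.2 requires.
- *Reading B: headings taken literally, cell 8 = Week 8, cell 9 = follow-up.* Laboratory tests are 6 and pregnancy tests 4. Blood volume is 6 × 15 + 4 × 5 = 110 mL against the stated 90. The pad test, urinary flow and residual urine would have no Week 8 mark.

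Only Reading A fits.

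**3. The ECG row under Reading A.** Cell 1 is enrolment in the observation period, cell 3 enrolment in the treatment period, cell 8 follow-up and cell 9 discontinuation. Cells 5 and 7 are empty. Scheduled post-baseline ECGs for a completer are therefore Week 4 = 0, Week 8 = 0 and follow-up = 1.

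**4. Table 5-2.** Its ECG row has the same cells (1, 3, 8, 9), but so does its pad-test row, which belongs at Week 8. Its laboratory and vital-sign rows have 5 marks, against 6 in the Synopsis. The Week 8 and follow-up columns have evidently collapsed into one. The table still shows that there is no Week 4 ECG and only one scheduled post-baseline ECG besides the discontinuation mark. Whether that ECG is at Week 8 or at follow-up cannot be read from the text.

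**5. Size.** Follow-up at 2 to 4 weeks is 2 × 7 = 14 to 4 × 7 = 28 days after the last dose. With the planning assumption of about 5% withdrawal among 250 patients, 0.05 × 250 = 12.5. So some 12 or 13 patients in all, about 4 per group (12.5/3 = 4.2), could have a discontinuation ECG near dosing. The remaining 237 or 238 would have none on drug.

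**The case against.** The strongest objection is that everything turns on the position of one mark in a damaged table. The table's own headings would put that mark at Week 8. Marks have moved elsewhere: the drug-prescription row falls in cells 2, 3 and 6 in the Synopsis but in 1, 3 and 5 in Table 5-2. The anchors calibrate the columns from other rows and cannot prove that the ECG mark stayed in place.

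Part of this stands. Table 5-2 is the schedule that section 5.1.8 cites, and its text is equally compatible with a Week 8 ECG, so a reader should not infer that the absence of an on-treatment ECG is established. But the headings fail the blood-count check. The displaced prescription row contains a sub-label that takes up a cell, which the ECG row does not. The rows directly above and below the ECG row keep cells 7 and 8 apart.

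Other stronger readings are tempting and are not supported:

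- *That no patient has any other post-baseline ECG.* The discontinuation mark gives early stoppers one.
- *That cardiac effects go unobserved during dosing.* Blood pressure and pulse rate are scheduled at Weeks 4 and 8 and tested against placebo in SAP 8.3.4, and adverse events are checked at each visit. The heart-rate gap is therefore partial. The class tables in section 1.4.2 list no QT prolongation.
- *That the t-tests were always planned.* The protocol plans descriptive ECG tables only; the tests entered in SAP Version 3.0 as an additional analysis.
- *That exposure at follow-up can be quantified.* The half-life is not visible, so no residual concentration can be given.

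Safety and design rationale are redacted in places, and section 14.2 reports that multiple dosing up to 6 mg was tolerated without safety problems. A reason for sparse ECGs may exist. It would not make an off-drug ECG informative about QTcF on drug.

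**Conclusion.** The point holds conditionally, with moderate confidence. In Synopsis Table 2, under the only column reading that fits Table 7.2-1 and section 2.3.2, a completer has no scheduled ECG during treatment and one at 14 to 28 days after the last dose. If the original Table 5-2 agrees, the ECG change tables and t-tests in SAP 8.3.3 describe completers off drug and cannot show an on-drug QTcF effect, whatever their result.

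This rests on the ECG mark not having shifted in the Synopsis text. If the original table shows a Week 8 ECG, the QTcF concern falls away. What would then remain is that SAP 8.3.3 does not name its ECG time points or say how discontinuation ECGs enter the analysis.

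**What to change.** 1. Check the ECG row in the original Table 5-2.
2. If it matches the Synopsis, reconcile Synopsis Table 2, Table 5-2 and SAP 8.3.3 so that the post-baseline ECG used for the drug-placebo comparison falls within the dosing period, at a visit patients already attend. Week 8 already includes vital signs and laboratory tests.
3. In SAP 8.3.3, name the ECG time points, as 8.3.5 and 8.3.6 do for their measures, and state how discontinuation ECGs are used.
4. Report any follow-up ECG as off-drug, and do not present it as evidence that there is no effect on treatment. If ECGs have already been collected on the Synopsis schedule, this relabelling is the part that can still be done.

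**Cost.** Moving the existing ECG adds no procedure but loses the post-drug recording; keeping both adds one ECG per completer. The SAP changes are a few lines.
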